The goal of this study is to determine whether addition of routine resistance testing, to guide management of virologic failure and sustain the successful completion of the HIV continuum of care, improves clinical outcomes and reduces costs for patients with virologic failure on first-line therapy in sub-Saharan Africa. We will enroll patients in care at public HIV clinics in Uganda and South Africa who have virologic failure on a first-line ART regimen, into a randomized controlled trial to complete the following aims:

- 1) Aim 1: Estimate the effectiveness of resistance test-based management of virologic failure (resistance testing arm), versus viral-load based management per WHO guidelines (standard of care arm).** We hypothesize that resistance testing-based management will be superior to standard of care management as measured by the proportion of patients with undetectable viral load 9 months after detection of virologic failure.
- 2) Aim 2: Evaluate the cost effectiveness of resistance-test versus viral load-based management of virologic failure in sub-Saharan Africa.** We hypothesize that resistance testing will be cost effective, because the cost of the assay will be offset by downstream cost savings through reduced use of second line therapy.

We intend that results of this study will be a useful resource for public health programmers, ministries of health and multinational partners to optimize the clinical management of virologic failure in the region.

[figure not shown]
III. BACKGROUND AND SIGNIFICANCE

In an effort to optimize the global HIV care continuum and foster sustained control of the HIV epidemic, the Joint United Nations Programme on HIV/AIDS (UNAIDS) has set a “90-90-90” treatment target for 2020 [2]. Achievement of this goal would mean, in part, that 90% of those receiving antiretroviral therapy (ART) sustain an undetectable HIV RNA viral load (viral load). At the epicenter of the epidemic in sub-Saharan Africa, however, rates of virologic suppression remain well below that goal; indeed, a systematic review of virologic suppression in the sub-Saharan African region found that only 2 in 3 patients maintain virologic suppression over two years of observation [3]. To maintain the goal of achieving 90% sustained virologic suppression, management of virologic failure must be optimized.

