The study design is an open-label, randomized controlled trial. The study will be conducted at study sites in Uganda and South Africa. The study population will include HIV-infected patients on first-line antiretroviral therapy with a recent viral load >1,000 copies/milliliter (mL). Eligible participants will be randomized to the WHO-based standard of care for management of virologic failure or immediate resistance testing with use of results to guide ART regimen decisions. The study will add the use of a diagnostic test, HIV-1 RNA resistance testing to clinical management of participants in the resistance testing arm, but all other clinical care including provision of ART therapy will be done by clinic sites in keeping with local HIV guidelines. The primary outcome of interest will be viral suppression (<200 copies/mL) at 9 months after study enrollment, and will be assessed using an intention to treat analysis, where missing or absent results will be considered failures. Secondary outcomes of interest will be viral suppression below the limit of assay detection, viral suppression on continuation of first-line (non-nucleoside reverse transcriptase inhibitor [NNRTI]-based) therapy, drug resistance at study conclusion, and mortality, among others. We will analyze primary data collected during the trial to conduct an economic analysis with the goal of estimating the cost-effectiveness of resistance testing versus standard of care.

B. Study Sites

1. Uganda

The Immune Suppression Syndrome (ISS) clinic at the Mbarara Regional Referral Hospital (MRRH) and its partner clinic across the street, the **Mbarara Municipal Clinic**, are PEPFAR-supported clinics, which, in combination, follow more than 20,000 patients with HIV/AIDS and have an established clinical research infrastructure. The clinics employ over 50 clinical care staff including nurses, clinicians, pharmacists, counselors, phlebotomists, patient trackers, and administrative staff. The clinics serve as the primary research sites for the MGH-MUST Global Health Collaborative, which employs an additional 60 research staff with expertise in recruitment, enrollment, participant monitoring, informed consent, data collection, phlebotomy, and laboratory storage and testing.

2. South Africa

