To assess our sample size calculation, we first estimated predicted rates of viral suppression in the SOC arm (Figure 3). To do so, we combined estimated suppression rates for those who remain on first line therapy and those who are switched to second line therapy, due to a persistent elevation in viral load >1,000 copies/mL. Multiple studies have reported that approximately 40% of people (range 27% - 59%) with an initial detectable viral load on first-line therapy load will re-suppress while remaining on first line therapy in the interim [2, 8-10]. Among those who do remain on first-line therapy, we estimate that only approximately 50% will remain suppressed on first-line therapy, owing to both high rates of underlying resistance [8], and sub-optimal adherence. Among patients in the SOC arm with persistent virologic failure on repeat testing who are switched to second line therapy, we expect approximately 80% will re-suppress [35]. In summary, we predict that net re-suppression rates in the standard of care arm compiling those who remain on first-line therapy (20%) and those who switch to second line therapy (48%), will be approximately 68%. While comparative rates of re-suppression with resistance testing are unknown, we hypothesize that resistance testing has the potential to significantly improve viral suppression rates, particularly because rates of resistance at first-line failure are common in the region (65-90%) [7, 8, 36], and because those who are switched to a protease inhibitor-based combination regimen are highly likely to re-suppress [37-39].

Figure 3. Schema of estimated outcomes for participants in the standard of care arm.

Assuming a 68% viral suppression rate in the SOC arm, using a two-sample test of binomial proportions with a Type I error rate of 5%, and allowing for a 5% rate of invalid tests, we compute a 69%, 88%, and 97% power to detect a difference in suppression rates of 8, 10, and 12%, respectively (Table 3). Based on these estimates, we plan to enroll approximately 840 total participants into the study to allow sufficient power to detect a programmatically meaningful 10% superiority rate of viral suppression in the RT arm.

Table 3. Sample Size Estimates

Viral Suppression Rate in SOC Arm	Viral Suppression Rate in RT Arm	Difference in Outcome Rate	α	Sample Size (per group)	Invalid Test Rate	Power
68%	76%	8%	0.05	420	5%	0.69
68%	78%	10%	0.05	420	5%	0.88
68%	80%	12%	0.05	420	5%	0.97

B. Efficacy Analyses

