The goal of this analysis is to estimate total projected costs for treatment programs, comparing the WHO standard of care versus a resistance-testing based approach to management of virologic failure. We will follow International Society of Pharmacoeconomics Outcomes Research (ISPOR) guidelines to develop models to determine the budget impact of adopting resistance testing in South Africa and Uganda, respectively ^[42]. We will populate each model with data provided by the clinical trial on costs of care, and add country-specific HIV epidemiology, demographic and expenditure data to estimate the budget impact of adopting resistance testing over five years for each strategy. We will build the model such that country-specific fields will be flexible to enable analysis with other countries, to facilitate policy planning

and decision-making. Results of this analysis will advise HIV program partners on the net resources required in each country to implement routine resistance testing over a 5-year period.

2. Cost Effectiveness Analysis

If the resistance testing intervention is superior or similar to the standard of care strategy, we will proceed with a full cost-effectiveness analysis. This analysis seeks to build upon prior analyses that have considered the economics of resistance testing in sub-Saharan Africa [22-24]. We will achieve this by incorporating primary efficacy, quality of life, and cost data from the clinical trial, and by estimating the cost utility of resistance testing versus standard of care by selecting quality adjusted life years (QALY) as our primary outcome of interest.

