To do so, we will develop a cost utility model in accordance with best practice recommendations for modeling from the ISPOR Good Research Practice Task Force [43] and will follow the guidelines set out by the National Institute For Health and Clinical Excellence Reference Case [44]. We will develop a decision tree cohort Markov Model using TreeAge (TreeAge Software, Inc., Williamston, MA) with methods similar to those previously described by Rosen *et al* in their analysis of the cost effectiveness of resistance testing-based management of virologic failure [23]. The outcome of interest will be the cost per QALY (\$/QALY), presented as an incremental cost-effectiveness ratio. We will populate the model for the first 9 months with comparative efficacy, health-related quality of life (EQ5D questionnaire), and resource allocation data derived directly from the clinical trial. We will value health-related quality of life using the time trade off approach for a reference population in sub-Saharan Africa as adopted in similar HIV-related cost-effectiveness analyses [45]. Thereafter, we will use published data on the natural history of HIV disease to model clinical outcomes every 6 months after study conclusion over a patient's lifetime, including risk of opportunistic infections, hospitalization, quality of life and death [46-50].

We will vary the probability of each outcome by CD4 category, presence (or not) of detectable viral load and presence (or not) of resistance, to extrapolate cost utility (Table 7). To characterize uncertainty in the model, we will conduct a probabilistic sensitivity analysis (PSA), and present data as cost-effectiveness acceptability curves and PSA plots. Convergent validity will be undertaken to compare the model to similarly published models on the cost effectiveness of resistance testing. Whereas results will be immediately relevant for the South African and Ugandan populations, the proposed structure of the model will be designed such that it may be used for adaptation to countries with similar health care contexts. Results will be presented in US dollars to inform foreign stakeholders.

XI. HUMAN SUBJECTS CONSIDERATIONS

A. Study Risks and Discomforts

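### The full cost-effectiveness analysis is conditional on resistance testing proving 'superior or similar', an undefined condition that Aim 2 does not carry

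*Combined protocol and SAP*

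**What the plan says.** Aim 2, in the opening statement of goals, is to "Evaluate the cost effectiveness of resistance-test versus viral load-based management of virologic failure in sub-Saharan Africa". The hypothesis attached to it is that testing will be cost effective "because the cost of the assay will be offset by downstream cost savings through reduced use of second line therapy". Section IV.A (Overview) repeats the purpose, an economic analysis "with the goal of estimating the cost-effectiveness of resistance testing versus standard of care". Neither place attaches a condition.

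Section X.C.2 (Cost Effectiveness Analysis) does: "If the resistance testing intervention is superior or similar to the standard of care strategy, we will proceed with a full cost-effectiveness analysis". It does not say on which outcome the arms must be similar, by what margin, or by what rule. It names no analysis for the case where RT is worse.

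The analysis behind this condition is a lifetime model: "The outcome of interest will be the cost per QALY (\$/QALY), presented as an incremental cost-effectiveness ratio". For uncertainty, "we will conduct a probabilistic sensitivity analysis (PSA), and present data as cost-effectiveness acceptability curves and PSA plots".

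Two economic items are not conditional: the five-year budget impact analysis (Section X.C.1) and total patient care costs over the study (Section X.B.3, item d). Both report costs only.

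**The concern.** Whether a strategy is cost-effective depends on the difference in cost and the difference in health effect together. A strategy that costs less and does slightly less well is a legitimate result on the cost-effectiveness plane, and a decision maker needs the ratio to judge it. Making the analysis depend on efficacy alone removes that part of the plane before costs have been examined. Efficacy in this trial is mainly viral suppression at 9 months. The economic outcome is lifetime QALYs, modelled on CD4 category, detectable viral load and resistance, so a small suppression deficit does not determine its sign or size.

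Because 'similar' is undefined, the decision would be taken with the efficacy result in hand, in an open-label trial. The primary comparison is a two-sample test of proportions sized for a 10-point gain, and no similarity margin is stated anywhere.

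At stake is whether one of the two stated aims is answered in its own terms. If a ratio is produced only when efficacy looks acceptable, the efficacy estimate feeding it is also a selected one.

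**Working it through.** **Inputs.** From Section X.A: 420 per arm, 68% suppression in SOC, 5% type I error, 5% invalid tests. A two-sided test is assumed.

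**The plan's own figures.** The SOC rate reproduces: 0.40 × 0.50 + 0.60 × 0.80 = 0.68. With 420 × 0.95 = 399 per arm and a pooled two-proportion z-test with continuity correction, power for differences of 8, 10 and 12 points is 0.684, 0.875 and 0.967. The plan states 0.69, 0.88 and 0.97, so the sample size section is sound. The condition in Section X.C.2 has no figure of its own to reproduce.

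**Precision.** All 420 per arm are used, because the primary analysis counts missing results as failures.
- True difference 0: SE = √(2 × 0.68 × 0.32 / 420) = 3.22 points. The 95% CI half-width is 1.96 × 3.22 = 6.3 points.
- True difference -3 (RT 65%): SE = √((0.68 × 0.32 + 0.65 × 0.35) / 420) = 3.26 points.

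**Chance that the analysis proceeds.** The documents define no rule, so two readings of 'similar' are assumed. With true difference δ and a cut-off c for the estimate, the probability is 1 − Φ(a), where a = (c − δ)/SE.

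| Reading (assumed) | True difference | c (points) | a | P(proceeds) |
|---|---|---|---|---|
| RT not significantly worse | 0 | -6.31 | -1.96 | 98% |
| RT not significantly worse | -3 | -6.38 | -1.04 | 85% |
| 95% CI excludes -10 | 0 | -3.69 | -1.15 | 87% |
| 95% CI excludes -10 | -3 | -3.62 | -0.19 | 58% |

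The first cut-off is -1.96 × SE (pooled). The second is -10 + 1.96 × SE. With 399 per arm, the two probabilities at -3 become 86% and 55%, so the invalid-test allowance hardly matters.

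**Shift in the efficacy input.** Among trials that pass the condition, the mean estimate exceeds the true difference by SE × φ(a) / (1 − Φ(a)). Under 'not significantly worse':
- True difference 0: 3.22 × 0.058 / 0.975 = 0.2 points.
- True difference -3: 3.26 × 0.232 / 0.851 = 0.9 points.

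Both shifts favour RT.

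**What remains if the condition is not met.** Costs (Section X.B.3 item d and Section X.C.1), suppression, and change in quality of life (Section X.B.3 item g) would each be reported. None of these is a cost per QALY, which is the outcome Section X.C.2 sets for the cost-effectiveness question.

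**The case against.** The strongest reply is that this is a matter of staging. The trial hypothesises superiority, and putting a lifetime model behind a 'not worse' result is a choice of scope that touches no test, sample size or stated power. The sentence says 'if', not 'only if', and it conditions a 'full' analysis. Aim 2 and the Overview still commit the investigators to cost-effectiveness. Trial costs, quality of life and suppression are reported regardless, and the primary result would show readers that the condition had failed. Under the lenient reading, the analysis almost always proceeds when the arms are truly equal.

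Much of this stands. It limits the loss to the modelled cost-per-QALY result and makes that loss possible rather than certain. It does not supply a definition of 'similar' or name an analysis for the other case.

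A reader might go further and infer that the condition would block exactly the scenario Aim 2 describes, because second-line patients suppress at 80% and first-line patients at 50%, so that fewer switches must lower suppression. The documents do not support this. In Section X.A the 50% belongs to SOC patients kept on first line, and it is attributed partly to underlying resistance; Section VI.B keeps on first line those without significant resistance. Section X.A also puts resistance at 65–90%, against 60% switched in SOC. If everyone with resistance switched, switching would rise, and even with the same two rates suppression would be 0.65 × 0.80 + 0.35 × 0.50 = 69.5% up to 0.90 × 0.80 + 0.10 × 0.50 = 77%, both above 68%.

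Nor can a saving be read off the regimen prices in Section III. There, 816 − 305 = $511 per year, so a 10-point fall in switching would save about $51 per person-year in drugs. That omits the assay, for which the same section cites $30, $100 and $242. Over 9 months the drug saving is 0.75 × 51 = $38, less than a $100 or $242 test.

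**Conclusion.** The point holds in this form: Section X.C.2 adds an undefined efficacy condition to an aim stated without one, and following it can leave the cost-per-QALY question unanswered when RT is somewhat less effective. At a true difference of -3 points, the chance that no such analysis is done is about 15% or 42% under the two readings examined. That spread comes from one undefined word. The probabilities rest on 68% suppression in SOC, a normal approximation, and margins the plan does not state.

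The selection effect is real but modest under the lenient reading, so it would overstate the matter to call any resulting ratio seriously biased. The documents also do not establish that a cheaper, less effective RT arm is the likely outcome; it is a possible result that the plan should be able to report. The primary efficacy analysis, the sample size and the stated power are unaffected.

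**What to change.** Delete the condition in Section X.C.2 and put in its place wording such as: *The full cost-effectiveness analysis will be carried out whatever the primary efficacy result. The estimated difference in suppression and its uncertainty will enter the probabilistic sensitivity analysis, and results will be shown on the cost-effectiveness plane, including the quadrant where resistance testing costs less and is less effective.*

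If the sponsor prefers to keep a condition, its outcome, margin and decision rule should be fixed before results are seen, and the analysis for the other case should be named.

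The change is one passage of text. EQ5D, resource-use and efficacy data are already collected, and the sensitivity analysis is already planned. Sample size stays at 840 and power is unchanged. The downside is that the modelling work is done even if resistance testing proves clearly worse.
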